The proposed protocol outlines a pioneering approach (Figure 1) - a pragmatic cluster randomized trial comparing the effectiveness and safety of dapagliflozin and empagliflozin seamlessly integrated within the Epic (Sundhedsplatformen) electronic health record (EHR) platform, currently operational in Eastern Denmark (Region Hovedstaden and Region Sjælland). The cluster randomized nature allows treatments to be assigned within patient clusters, mitigating the logistical challenges associated with individual patient randomization. Notably, this novel setup streamlines trial enrollment, ensuring prompt recruitment, cost-efficiency, and minimal disruptions for both healthcare providers and patients, in contrast to traditional randomized trials (Figure 2). Pragmatic alludes to the inclusion of patients from real-world clinical practice and the endpoint ascertainment from administrative registries. As opposed to traditional trials, this setup improves generalizability of the findings and eliminates the need for in-person follow-up visits. This study represents

an important step forward for medical evidence-generation, not only delivering important clinical insights into head-to-head differences of SGLT2 inhibitors, but also serving as a proof-of-concept model for forthcoming trials within this innovative framework. Ultimately, APPLE TREE (A Pragmatic Trial Comparing Empagliflozin and Dapagliflozin Through Cluster Randomization Embedded in an Electronic Health Record Platform) has the potential to improve care and inform treatment decisions for the millions of patients globally affected by T2D, HF, and CKD.

Hypothesis

We hypothesize that there will be no significant difference in the effectiveness and safety of dapagliflozin and empagliflozin.

Primary objective

To evaluate comparative effectiveness of dapagliflozin versus empagliflozin on the risk of all-cause mortality, HF hospitalization, myocardial infarction, ischemic stroke, and incident or worsening nephropathy.

Secondary objectives

To evaluate the risks of individual effectiveness and safety outcomes for dapagliflozin vs empagliflozin. Furthermore, to determine differences in risks for dapagliflozin vs empagliflozin in relevant subgroups.

Trial design

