Based on extrapolations from Danish registry data spanning from 2018 to 2021 (Figure 3), we estimate that 8,600 patients (of whom 30% and 15% will have HF and CKD, respectively), will initiate treatment with dapagliflozin or empagliflozin per year in Region Hovedstaden and Region Sjælland. This will result in randomization of 17,200 patients (8,600 per group) over 2 years. Based on the registry data, we assume a 19% event rate of the primary endpoint during 2 years of follow-up. This will yield 90% power to detect an absolute reduction of 1.9% (corresponding to a 10% relative reduction) in the 2-year rate of the primary endpoint at a statistical significance level of 5%. The expected width of the 95% confidence interval is 2.3%; in other words, the trial can establish that any difference is not larger than 2.3% on the risk difference scale.

Subgroups

We will analyze the primary endpoint in the following subgroups:

- Patients with T2D
- Patients with HF
- · Patients with CKD
- Age <65 years/age ≥65 years
- Males/females

Randomization and blinding

The randomization will be done in clusters which in the present study will consist of 1-hour time frames (Figure 1). In random order, every hour, the treatment assignment will be either dapagliflozin or empagliflozin. A generic module will be developed that allows direct cluster randomization through Epic (Sundhedsplatformen), the EHR platform currently used in Region Hovedstaden and Region Sjælland. The module will alert the physician to the treatment assignment of the current time frame (cluster) when she places a prescription (best./ord.) for either dapagliflozin or empagliflozin. As an example: when a physician makes a prescription for empagliflozin between 11.00 and 11.59 am on a given day, the

randomization module will alert the prescribing physician to which treatment is assigned at the present time frame (cluster). The next hour, the assignment may stay the same or change from e.g., empagliflozin to dapagliflozin in a random fashion. As such, treatment allocation is concealed to patients and caretakers until randomization. In this study design, blinding is not possible to patients and caretakers, but treatment assignment will be concealed to the data collectors and the responsible statistician until the final trial database is locked.

Statistical analyses

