Potential participants will be identified when they are admitted to the hospital and have indication for treatment with dapagliflozin or empagliflozin as per usual practice. The participating departments will include patients automatically through the Sundhedsplatformen (Epic) prescription module for cluster randomization. This means that only patients who would have received dapagliflozin or empagliflozin regardless will be subject to randomization. As such, no screening of health records will be performed to identify study participants. Likewise, treating physicians (not limited to the prescribing physician) have discretion to halt or change the assigned treatment, regardless of inclusion in the trial, as per usual practice. Follow-up will be conducted through automatically collected registry data, resulting in no additional study visits or collection of additional non-standard data from patients. Information about the study will be provided through a pamphlet which will be handed to the patient, who can choose to opt out by informing clinical staff at the trial site orally. If a patient chooses to opt out, the treating physician will simply click a button (specifically designed for opt-out) in the randomization module in

Sundhedsplatformen and proceed to prescribe the preferred treatment, as per usual practice. The withdrawal of consent will then be automatically registered. Enrollment only occurs when the randomization is accepted in Sundhedsplatformen. As such, patients who opt out at this point will not be enrolled in the study and none of their data are collected. According to Danish and EU-legislation, informed consent can be obtained by simplified means when a cluster randomized study is conducted.

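### The full width of the expected 95% confidence interval (2.3 points) is presented as an unconditional limit on the difference between the drugs; it is a limit only when the result is non-significant, and even then it does not rule out the 1.9-point design difference

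*Protocol*

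**What the plan says.** The protocol's section Sample size and power sets out a two-group comparison of 2-year risks:

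- Size: "This will result in randomization of 17,200 patients (8,600 per group) over 2 years".
- Event rate: "we assume a 19% event rate of the primary endpoint during 2 years of follow-up".
- Power: "This will yield 90% power to detect an absolute reduction of 1.9% (corresponding to a 10% relative reduction"), "at a statistical significance level of 5"%.
- Precision: "The expected width of the 95% confidence interval is 2.3%; in other words, the trial can establish that any difference is not larger" than 2.3 points on the risk-difference scale.

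The precision statement carries no condition on the observed result. The Hypothesis section reads: "We hypothesize that there will be no significant difference in the effectiveness and safety of dapagliflozin and empagliflozin". The Statistical analyses section names an intention-to-treat Cox model reporting hazard ratios with 95% confidence intervals. The protocol sets no equivalence or non-inferiority margin and does not call the 2.3 points a margin.

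**The concern.** The width of a confidence interval measures precision. It says nothing about where the interval will lie, so it cannot by itself limit the size of the difference. The protocol nevertheless moves from a width of 2.3 points to a claim that differences above 2.3 points will be ruled out, whatever the data show.

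This matters because a null result is what the protocol expects, and the sentence is its only link from such a result to a statement about how different the drugs could still be. A reader who relies on it would take the trial to guarantee a limit that it does not guarantee. They could also overlook that the limit, where it does hold, is wider than the 1.9-point difference used for sizing in the same paragraph.

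**Working it through.** **Inputs, all from Sample size and power:** n = 8,600 per group; 2-year risk 19.0%; design difference 1.9 points, so 17.1% in the other group; significance level 5%. Sidedness is not stated. Two-sided is assumed because it reproduces the stated power. Like the protocol's own figures, the check makes no allowance for clustering and assumes complete 2-year follow-up.

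**1. Reproduce the protocol's figures.**

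- SE = √(0.19×0.81/8,600 + 0.171×0.829/8,600) = 0.00586, or 0.586 points.
- Power = Φ(0.019/0.00586 − 1.96) ≈ 0.90, as stated. A one-sided 5% test would give 94.5%.
- Sample size for 90% power: 8,609 per group, against 8,600 stated.
- Full 95% width = 2 × 1.96 × 0.586 = 2.30 points; half-width 1.15.
- With 19% in both groups: SE = √(2×0.19×0.81/8,600) = 0.598 points; full width 2.35, half-width 1.17.

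The stated 2.3 is therefore the full width, from lower to upper limit.

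**2. What the interval excludes, by observed difference.**

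| Observed difference (points) | 95% interval (points) | Differences excluded |
|---|---|---|
| 0 | −1.17 to 1.17 | beyond about ±1.2 |
| 1.15 to 1.17 (just non-significant) | 0 to 2.30–2.35 | above about 2.3 |
| 1.9 (the design difference) | 0.75 to 3.05 | above about 3.05; 2.3 is not excluded |

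The general rule is simple. If the interval contains zero, its far limit cannot exceed the full width. If it excludes zero, its far limit must exceed the full width.

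**3. How often the statement would come true.** Take SE = 0.598 and half-width h = 1.17, and let d be the true difference. The chance that the whole 95% interval lies within ±2.3 is Φ((2.3 − h − d)/SE) − Φ((−2.3 + h − d)/SE):

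| True difference (points) | Chance |
|---|---|
| 0 | 94% |
| 0.5 | 85% |
| 1.0 | 58% |
| 1.9 | 10% |

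The last row also follows from the protocol's own power. With a true difference of 1.9 points, about 90% of trials give a significant result, and in those the far limit exceeds the full width.

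**4. Compare the limit with the design difference.** A just non-significant interval of about 0 to 2.3 meets the protocol's statement and still contains 1.9. With a true difference of exactly zero, the chance that the 95% interval lies within ±1.9 is 2Φ((1.9 − 1.17)/0.598) − 1 = 78%. About 22% of such trials would therefore fail to exclude 1.9. With a 90% interval (1.645 in place of 1.96) the chance is 87%.

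**The case against.** The strongest defence is that the sentence is meant for the expected outcome. If the result is non-significant, the interval contains zero and 2.3 points is the worst case left open. The 94% at a true difference of zero fits this, being close to the 95% chance of a non-significant result. The example with an estimate of 1.9 is a significant result, for which the trial would report a difference and not similarity. All of this stands.

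It follows that a reader who infers a factor-of-two error, with 1.2 as the right limit and 2.3 as a slip, goes too far. The 1.2 applies only to an estimate of zero. Non-significant results leave open a largest difference of anything from about 1.2 to 2.3 points. What the defence cannot supply is the missing condition, since the protocol makes the statement about any difference.

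A second defence is that the primary objective is neutral, the hypothesis is only an expectation, and rules of interpretation may sit in the statistical analysis plan. This also stands in part. A reader might infer that the trial intends to declare equivalence from p > 0.05, but the protocol does not say so. The lack of an equivalence margin is therefore not in itself an error here.

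A reader might also infer that treatment changes undermine a null result, because treating physicians "have discretion to halt or change the assigned treatment, regardless of inclusion in the trial, as per usual practice". Switching between the drugs would tend to pull an intention-to-treat estimate towards zero. The protocol gives no switching rate, however, so no size can be put on this, and whether to add an on-treatment analysis can be left to the analysis plan.

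**Conclusion.** The precision sentence is wrong as written. The 2.3 points is correctly computed as the full width, but it limits the difference only if the result is non-significant, and the protocol omits that condition. Without it, the chance of the claim coming true runs from 94% at no true difference down to 10% at the protocol's own design difference.

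Even with the condition supplied, the limit leaves a 1.9-point difference open. A non-significant result alone would therefore not be evidence of similarity in the sense that the Hypothesis section invites.

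The point concerns interpretation only. The sample size and the 90% power are reproduced and unaffected. The figures assume a two-sided 5% level, 8,600 per group, a 19% risk, complete 2-year follow-up and no clustering effect. They also take non-significance to mean that the risk-difference interval contains zero. The named Cox model tests the hazard ratio, so the two may differ slightly in a borderline case.

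**What to change.** Replace the precision sentence with:

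> The expected 95% confidence interval for the 2-year risk difference is the estimate ±1.2 points (full width 2.3). If the observed difference is zero, differences above about 1.2 points are excluded; if the result is non-significant, differences above about 2.3 points are excluded.

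Add that similarity will be judged from the confidence limits of the 2-year risk difference and not from a p-value above 0.05. This means that the risk difference must be reported alongside the hazard ratio.

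If the sponsor wants to be able to conclude equivalence, it should name a margin, and the power at that margin, before unblinding. As an illustration only, ±1.9 points at a true difference of zero has 78% power with a 95% interval and 87% with a 90% interval. The protocol does not call 1.9 points an acceptable difference, so the choice of margin is the sponsor's. If no equivalence claim is intended, the hypothesis can be reworded as an estimation aim.

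The cost is protocol wording and one additional reported estimate, with no change to size, randomisation or endpoints. The one drawback is that a named margin may not be met.

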To ensure that all participants understand the written material, this will be available in multiple languages by authorized translations. The information will be written in lay terms and will comply with what is described in the protocol and will state that the patients can refuse to participate and can withdraw at any time. If the patient is permanently incapable of understanding the written material, this patient will not participate in the study. Examples of such conditions include severe dementia or mental deficiency. The treating physicians at the trial sites will be instructed to not enroll patients in the study if they fulfill this criterion according to their own discretion. In addition, it will be pointed out that opting out will not have any influence on the patient's further treatment. One month after patients have been discharged or their outpatient contact has ended, they will also receive an email through E-boks describing that they have been included in the study and that they can choose not to participate in the study by actively withdrawing their consent. Additionally, if concerns arise regarding safety, guideline-changes, or significant price changes (threefold or more) of the investigational medicinal products, an update will be sent to study participants through E-boks.

The nurses and doctors will have received both oral and written material regarding the study, which will make them capable of answering questions regarding the study. Either the doctor or the nurse will hand out the written material to the patient (Appendix).

Consent

As of January 2022, a new regulation (EU regulation No 536/2014 of the European parliaments and of the council of 16th of April 2014 on clinical trials on pharmaceutical products for human use article 30 (informed consent in cluster trials)) has been implemented, that allows for omission of traditional informed consent in cluster randomized trials. Likewise, corresponding Danish legislation was implemented on January 1st, 2024 (LOV nr 1776 af 28/12/2023). As such, informed consent can be given based on written material, and lack of objection from the trial participants is considered as informed consent. Practically, this means that participants are given written information in accordance with the protocol, and that

the information material stipulates that the participant may refuse to participate in the study or withdraw at any point without any resulting detriment.

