Additional conditions must be fulfilled:

- a) The simplified means does not contradict national law.
- b) The methodology requires groups of participants rather than individual subjects (justified in section; Trial purpose).
- c) The clinical trial is low-intervention and that the pharmaceutical products are used in accordance with the terms of the marketing authorization (the study drugs are only investigated in patients with the indications specified in the marketing authorization, and are already used in everyday clinical practice, where the choice as of now is mainly being dictated by physician preference).
- d) There are no interventions other than the standard treatment of the subjects concerned.
- e) The protocol justifies the reasons for obtaining informed consent with simplified means and describes the information given to the patients.

Withdrawal of consent

Patients can choose to withdraw consent from the study and/or withdraw consent for usage of their data. If a patient withdraws, they will not enter the study and their data will not be used or analysed. Data regarding withdrawal will be collected via Sundhedsplatformen. The patients will be able to withdraw their consent at any time, including after the hospital contact has ended and will also receive an email via E-boks 1 month after discharge describing their participation in the study, potential significant price changes, and the possibility of withdrawing their consent. They will be instructed to notify their withdrawal of consent through secure email to [contact], which will be monitored by members of the executive committee.

Information material to patients

All patients will be given written information material when are prescribed one of the study drugs (Appendix). The information will be written in lay man terms and in different languages based on authorized translations, and will comply with what is described in the protocol and will state that the patients can refuse to participate and can withdraw at any time. In addition, it will be pointed out that opting out will not have any influence on the patient's further treatment.

Information to healthcare professionals and organization of trial sites

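### As the protocol reads, enrolment follows display of the assigned drug, so the intention-to-treat set is open to selection after allocation is known

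*Protocol*

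**What the plan says.** All references are to the protocol.

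- **Randomization and blinding.** The unit of allocation is the hour: "The randomization will be done in clusters which in the present study will consist of 1-hour time frames". On timing: "The module will alert the physician to the treatment assignment of the current time frame (cluster) when she places a prescription". The section concludes: "As such, treatment allocation is concealed to patients and caretakers until randomization". It also accepts that the trial is open: "In this study design, blinding is not possible to patients and caretakers".
- **Recruitment arrangements.** A patient may opt out orally. The physician then clicks a dedicated button in the randomization module and prescribes whichever drug is preferred. On entry to the trial: "Enrollment only occurs when the randomization is accepted in Sundhedsplatformen". Patients opted out at that stage are not enrolled and their data are not collected, although the withdrawal itself is registered automatically. Physicians are also "instructed to not enroll patients in the study if they fulfill this criterion according to their own discretion", the criterion being permanent inability to understand the written material. No time is set for that judgement.
- **Information material to patients.** "All patients will be given written information material when are prescribed one of the study drugs".
- **Withdrawal of consent.** Data of patients who withdraw are not used or analysed, and withdrawal is possible at any time, including long after the drug is known.
- **Statistical analyses.** The primary analysis follows the intention-to-treat principle.

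**The concern.** Randomization makes the two groups comparable only if the decision to include a patient does not depend on the drug drawn. Here the decision appears to come after the draw is on the screen, and it is entered by a physician who knows it. If some prescribers accept one drug less readily for certain patients, the arms will differ in case mix before treatment starts. An intention-to-treat analysis of accepted patients does not repair this, because the missing patients never entered the set.

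The protocol itself gives reasons why preference might play a part. Its Consent section says that the choice of drug is at present mainly a matter of physician preference, and the background cites small observational studies favouring dapagliflozin for cardioprotection. The trial hypothesizes no difference and looks for small effects, so a modest selection effect could create a spurious difference or hide a real one.

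**Working it through.** **Order of events.**

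1. The order is placed and the module shows the drug for the current hour (Randomization and blinding).
2. The physician either accepts or uses the opt-out button in that module (Recruitment arrangements).
3. Only acceptance enrols the patient.

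A randomization can be accepted only once it exists, and opting out at that stage points to the same moment. Written information is given at prescription, so the patient's own choice also falls around this step. Nothing in the text requires eligibility, capacity or opt-out to be settled before step 1.

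**Reach of the concealment sentence.** It protects allocation until randomization. It leaves two gaps: the interval between alert and enrolment, and any later order in the same hour by a prescriber who has already seen that hour's alert. Future hours are drawn at random and stay unpredictable.

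**The plan's own figure.** Sample size and power gives 8,600 per group, 19% versus 17.1% at two years, 5% significance and 90% power. The two-sided two-proportion calculation returns 89.97%, so the stated power is reproduced. The standard error of the risk difference under no effect is √(2 × 0.19 × 0.81 / 8,600) = 0.598 percentage points.

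**Illustration (assumed inputs, no true drug difference).** Let a share s of patients be high-risk, with two-year risk h; the rest have risk l. In one arm only, a fraction q of the high-risk patients is opted out. That arm's risk becomes

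[s(1 − q)h + (1 − s)l] / (1 − sq),

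and the bias is the overall risk minus this value. With z = bias / 0.598, the type I error is Φ(z − 1.96) + Φ(−z − 1.96).

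Example with s = 0.30, h = 0.35, l = 0.1214, q = 0.10: (0.30 × 0.90 × 0.35 + 0.70 × 0.1214) / 0.97 = 0.1851. The bias is 0.1900 − 0.1851 = 0.49 points, z = 0.83, and the type I error is 13%.

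| s | h | l | Bias, points (q = 5% / 10% / 20%) | Type I error (q = 5% / 10% / 20%) |
|---|---|---|---|---|
| 0.30 | 0.30 | 0.143 | 0.17 / 0.34 / 0.70 | 6% / 9% / 22% |
| 0.30 | 0.35 | 0.121 | 0.24 / 0.49 / 1.02 | 7% / 13% / 40% |
| 0.30 | 0.40 | 0.100 | 0.32 / 0.65 / 1.34 | 8% / 19% / 61% |
| 0.45 | 0.35 | 0.060 | 0.37 / 0.75 / 1.58 | 9% / 24% / 75% |

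The first three rows are set to an overall risk of 19.0%; the last gives 19.05%. The 0.45 adds the protocol's 30% with heart failure and 15% with CKD as if no patient had both, so it is an upper value for that group. The protocol states none of the risks h and l and no opt-out fraction. At q = 10% the affected arm loses 3% of its patients (4.5% in the last row).

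**Would it be seen?** If selection followed heart failure or CKD status, baseline data would show it. With s = 0.45 and q = 10%, the high-risk share in the affected arm falls to 0.405 / 0.955 = 42.4%. The standard error of the between-arm difference is √(2 × 0.45 × 0.55 / 8,600) = 0.76 points, so the gap of 2.6 points is about 3.4 standard errors.

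**The case against.** - **The screen order is inferred.** No sentence says whether the opt-out button appears before, with or after the assignment, and the figure that might show it is not available here. This stands as a limit. The wording points clearly one way, however, and if opt-out is meant to come first the protocol should say so.
- **A reader might infer that the bias could be neither measured nor adjusted for.** The documents do not support that. Opt-outs are registered, so counts should be obtainable, and enrolled patients have baseline data from the health record and registries. Selection on recorded factors such as heart failure or CKD could be detected and adjusted for, as shown above. Selection on unrecorded factors could not, and the characteristics of opted-out patients are not kept.
- **A reader might call the concealment sentence false.** It claims concealment only until randomization, and future hours are indeed unpredictable. It is too narrow rather than untrue. The same-hour gap is also small: 8,600 patients a year over 8,760 hours is about one per hour across all hospitals, or about four if prescribing is assumed to fall within 2,000 working hours.
- **Prescribers have another route.** They may change the assigned treatment after enrolment, and such patients stay in the intention-to-treat set. Opt-out is defined as the patient's choice, and the protocol asserts equipoise. This weakens the motive to misuse opt-out but does not block it.
- **A reader might also expect prescribers to cancel and re-order in the next hour, or repeat orders to draw the other drug.** That is conjecture about a module still to be developed. Inclusion is limited to new prescriptions, and nothing says that an enrolled patient would be randomized again. It supports a safeguard in the specification and is not evidence of a fault.

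**Conclusion.** The point holds in a limited form. As Randomization and blinding and Recruitment arrangements read together, inclusion is settled after the prescriber has seen the drug, and the concealment sentence does not cover that step. The intention-to-treat set is therefore open to selection; the documents do not show that selection will occur.

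The size is unknown. Opt-out unrelated to the assigned drug would cause no bias. With 10% of high-risk patients opted out in one arm only, the assumed scenarios give a spurious difference of about 0.3 to 0.75 points, against a design effect of 1.9, and a type I error of about 9% to 24%. The larger values in the table need 20% one-sided opt-out, for which the protocol offers no evidence, and should not be read as a forecast. At 5% the error rate is only 6% to 9%, so it would also be wrong to conclude that any small selection effect turns significant in a trial of this size.

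The matter deserves correction before enrolment because it bears on the validity of the primary comparison, can be prevented cheaply, and cannot be fully repaired later.

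**What to change.** 1. State in Randomization and blinding and in Recruitment arrangements that eligibility, capacity and opt-out are confirmed in the module before the assignment is displayed, with enrolment time-stamped at that moment. Define the intention-to-treat set as all patients enrolled at that point, whether or not the assigned drug is then prescribed, subject to later withdrawal of consent. Keeping in the analysis everyone who was shown an assignment, opt-outs included, would conflict with the protocol's consent rules; taking opt-out first largely avoids that conflict.
2. Store the first assignment displayed for a patient, so that a later order does not give a new draw.
3. Report anonymous counts of opt-outs, declined alerts and later withdrawals by assigned drug.
4. Reword the concealment sentence to match: allocation is hidden until eligibility and opt-out have been recorded, apart from what a prescriber may already know from an alert in the same hour.

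The cost is a change of click order in a module not yet built, plus protocol wording. One small downside: the pamphlet must be handed out before the order is opened rather than at prescription.
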